3.5.4 Safety/Tolerability Assessments

Safety monitoring after administration of study medication

All subjects will be kept under clinical observation for 24 hours after the first administration of study vaccine and for 4 hours after subsequent administrations of study vaccine (second, third and fourth administrations). During that period, the vital signs will be monitored and the injection site will be observed on regular basis. A physical examination will be performed prior to discharge. The clinical observation may be prolonged in case of safety concerns according to the clinical judgement of the investigator.

A subsequent safety assessment will also be performed 48 to 72 hours after each immunization by telephone call for all study subjects. An unscheduled visit should be proposed in case of moderate or severe suspected adverse reactions reported by telephone assessment, according to clinical judgement.

Physical and Neurological Examination

Physical examination will include assessment of general appearance, the head, eyes, ears, nose, throat, heart, chest, lungs, abdomen, lymph nodes, extremities, peripheral pulses, skin and any other physical conditions of note. Weight will be recorded in kg and height (first attempt) in cm. The neurological examination will include examination of the cranial nerves, upper and lower

extremities for muscle strength, reflexes, sensation and cerebellar function. Examinations will be performed at each visit at the center.

Vital Signs

Vital signs will be measured at each visit. During dosing visits, vital signs (blood pressure, heart rate, respiratory rate and temperature) will be measured before and after the administration of study vaccine. At V1 (baseline), measurements will be made just before the first injection (time 0) and at the following time after the injection at 1, 2, 4, 8, 12, and 24 hours. On subsequent dosing visits (V3, V5*, V8), measurements will be done at time 0, 1, 2, and 4 hours. *The vital signs assessment does not apply in case V5 is performed remotely in sub-cohort 1.1 subjects (refer to section 3.5.2.10).

Blood pressure and heart rate will be measured in the sitting and standing positions at the screening visit and at time 0 of V1 (baseline). The sitting blood pressure should be measured first and should be measured after the subject has been sitting down for at least 5 minutes. The subject should then be asked to stand and the standing blood pressure should be measured after the subject has been standing for 2 minutes. At all other time points for V1 or for all other visits, blood pressure and heart rate will be measured in the sitting position only.

Blood pressures will be measured with a standardized mercury manometer; alternative validated methods of measurement may also be used. The point of disappearance of Korotkoff sounds (phase V) will be recorded as the diastolic blood pressure where a sphygmomanometer is used.

Heart rate will be determined over 60 seconds following the recording of blood pressure in the corresponding position.

Body temperature will be measured and recorded.

Pregnancy Testing

In women of child bearing potential, blood pregnancy tests will be performed at the screening visit (blood draw between day -14 and day -3 prior to baseline). Subsequently, pregnancy tests from urine will be performed prior to the dosing. The test strips will be provided by the Central Laboratory.

Electrocardiogram (ECG)

12-lead ECG recording machines will be provided by the central reading company. Printouts of each ECG must be kept at the site for archiving. The central reading company will manage ECG data through their Web-based platform. The system allows the acquisition, storage and display of ECG recordings from the ECG machines so that cardiologists can review them. A manual describing all methods for collecting ECG data will be provided to the Investigator.

Magnetic Resonance Imaging (MRI)

Brain MRI scans will be conducted according to the schedule of assessments and examined for evidence of encephalitis and other brain pathology. Scans will be systematically analyzed e.g. for the presence of micro hemorrhages or vasogenic edema by the Central reading company. A manual describing all methods for collecting MRI data will be provided to the site.

Safety Blood and Urine Analysis

Tests for safety blood and urine analysis will be performed at the central laboratory. Details regarding handling, storage and shipment of the safety blood and urine samples will be provided to the study centers in writing (see Laboratory Investigator Manual).

Hematology

Safety hematological analysis will be performed at all visits. Analyses will include: red blood cell count, hemoglobin, hematocrit, red cell indices, white blood cell count (including differential), platelet count.

Coagulation indices (PT (INR)/aPTT) will be measured at the Screening Visit and at visits preceding the visits where the lumbar punctures take place.

Biochemistry

Safety biochemistry will be performed at all visits. Analyses will include:

Sodium, potassium, chloride, urea, creatinine, calcium, inorganic phosphate, glucose, total bilirubin, total protein, albumin, aspartate aminotransferase, alanine aminotransferase, alkaline phosphatase, Gamma GT, creatine kinase, cholesterol, triglycerides and uric acid and CRP.

Diagnosis of auto-immune diseases

Anti-Nuclear Antibody (ANA) and anti-double stranded DNA (anti-dsDNA) antibody titers will be tested at all visits. At dosing visits, the blood sample will be collected prior to injection of the study vaccine. A detailed assessment for lupus or other rheumatologic disease will be performed if the anti-ds DNA antibody test is positive. Subjects who have a positive anti-dsDNA antibody result and associated clinical symptoms will be discontinued from further immunizations but will be followed for safety. A DSMB review will be held to determine further immunizations on the study.

Safety Urine Analysis

Safety urine analysis will be performed at visits indicated in the schedule of assessments (section 3.5.1). Analyses will include: pH, protein, glucose, ketones and blood.

Inflammatory Markers in CSF

CSF samples will be obtained (as per the schedule of assessments of section 3.5.1) using standard lumbar puncture procedures performed by a physician experienced in the procedure who will ensure that the subject receives appropriate medical care after the procedure has been performed. Materials for and details regarding collecting and processing CSF samples will be provided to the investigator. CSF samples will be sent to Central Laboratory according to provided instructions.

The lumbar puncture which is conducted at screening should be performed at least 3 days prior to the administration of the study medication. This is to reduce the chance that any post-lumbar puncture headache might interfere with the assessment of adverse events occurring after administration of the study medication. The CSF samples will be examined for evidence of inflammation including:

- Protein
- CSF/serum albumin ratio
- IgG + IgM index
- Oligoclonal bands
- Glucose
- Cell Count and differential count when applicable (to be performed at the local site laboratory)

Screening Tests

The following tests will be performed on serum at screening visit only as part of work-up to rule out other causes of cognitive impairment: VDRL (Syphilis serology), Vitamin B12 and folate, Thyroid function tests (T4, T3, TSH), HIV. In addition Hepatitis B and C testing will be conducted.

Adverse Events

All AEs occurring after the subject signs the ICF and up to the last safety follow-up visit (V11 Week 74) or up to Visit 13 (Week 98) in case the post-injection period is extended, will be recorded.

See Section 4 for additional information.

Cognitive tests

The cognitive tests are used either to verify eligibility criteria or as part of the safety assessments to verify there is no impairment of subject cognitive status that could be related to the study vaccine. The tests have been selected as suitable for the degree of cognitive impairment in eligible subjects. Tests should be performed by a trained rater, who except for the cognitive rating activities is not involved in any other study-related activities. The rater should be a psychologist or other site personnel, experienced on psychometric tests, who should neither perform nor have access to any other subject clinical assessments during the course of the study. An experienced and adequately trained back-up rater should exist. Training on cognitive tests will be provided by

Whenever possible the cognitive tests should be performed at the same time of day throughout the study for each individual subject, i.e. ideally within a ± 2 hours-time window.

MMSE

The Mini Mental State Examination (MMSE) (Folstein 1975) is a widely used test of overall cognitive function, assessing memory, orientation and praxis in a short series of tests. The score is from 0 to 30 with 30 being the best possible and 0 being the worst possible score. The test will only be performed at the screening visit to confirm subject's eligibility to participate.

RBANS

The Repeatable Battery for the Assessment of Neuropsychological Status (RBANS) (Randolph, 1998) is a test designed to measure cognitive decline or improvement in a short series of 12 subtests that measure attention, language, visuospatial/constructional abilities, and immediate and delayed memory. The test yields 5 Index scores and a Total Scale score. Normative information from the test manual is used to calculate the Index and Total scores. Three versions of the scale are used during the study: form A (at V1 and V9), form B (at V6 and V11) and form C (at Screening).

Clinical rating scales

The clinical rating tests are used as part of the safety assessments to verify there is no impairment of subject clinical status that could be related to the study vaccine. The clinical rating scales should be performed by a trained clinical rater (experienced site personnel). The clinical rater should not perform the cognitive tests. Training on clinical tests will be provided by

C-SSRS

Recent guidance from the FDA has indicated the importance of collecting data on potential induction of suicidal behavior with all new agents acting on the central nervous system. Although no such effects are anticipated with the study vaccines investigated, this will be directly evaluated with the Columbia-Suicide Severity Rating Scale (C-SSRS) at several

time points during the study. Questions related to suicidal behavior or ideation are directly asked by the rater to the subject. Two versions of the questionnaire are used during the study: Baseline/Screening version (at Screening) and Since Last Visit Version (at V1).

CDR

The Clinical Dementia Rating Scale (Hughes et al. 1982) is a global rating of the function of AD subjects assessed in six categories: memory, orientation, judgement and problem solving, community affairs, home and hobbies and personal care. It is based on a semistructured interview conducted with the subject and caregiver, by a rater without access to the results of the cognitive tests described above. Each category has scores from 0 (no symptoms) to 3 (severe) and the sum of these items (sum of boxes) may therefore range from 0 to 18 points. The CDR global score is derived from scores of each individual category and will be used as part of the selection criteria (score of 0.5 or 1 at Screening).

NPI

The Neuropsychiatric Inventory (NPI) is a 12-item scale which assesses behavioral disturbances commonly occurring in dementia subjects. Twelve behavioral areas are included in the NPI: delusions, hallucinations, agitation/aggression, depression/dysphoria, anxiety, elation/euphoria, apathy/indifference, disinhibition, irritability/lability, aberrant motor behavior, night-time behaviors, and appetite/eating changes. Through a structured interview with the caregiver, each of these 12 domains will be assessed. Both the frequency (0-4) and severity (0-3) of each domain will be determined and multiplied together and summed across domains for a total score of 0-144; a higher score indicates more severe psychopathology.

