5.3.5.1 Cognitive/Clinical variables

The following variables will be included in the analyses:

- 1) Global function (change from baseline in CDR-SB (Clinical Dementia Rating Scale-Sum of Boxes)
- 2) Other cognitive tests (change from baseline in RBANS)
- 3) Behavior (change from baseline in NPI)
- 4) Columbia-Suicide Severity Rating Scale (C-SSRS) scores

Data will be presented per measurement time and dose group.

For endpoint 1), the baseline value is the score obtained at Screening except for subjects of subcohort 1.1 for which the baseline value is the score obtained at V1 [Week 0]. For other endpoints, the baseline value is the score obtained at V1 [Week 0]. Change from baseline [Week 0 or Screening] at Visit 6 [Week 10], Visit 9 [Week 50] and Visit 11 [Week 74] will be summarized per dose group.

For endpoint 4), individual narratives will be presented for all subjects who report serious suicidal intent or any suicidal acts during the study.

Where data on RBANS, CDR-SB and NPI have been collected remotely by telephone interview, at subjects' homes or by videoconference, specific sub-analyses will be conducted in order to explore the potential impact of the remote mode of administration on the related results.

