# 11.0 Statistical Methods

All analyses will use SAS® version 9.4 or higher. Descriptive summaries will be tabulated by treatment group (ACI 300µg, ACI 900µg, ACI 1800µg, JACI 15µg, JACI 60µg). Where applicable, all subjects from each main cohort will be summarized together (excluding immunogenicity and biomarker TFLs).

Categorical data will be presented using counts and percentages, with the number of subjects in each category as the denominator for percentages. Percentages will be rounded to one decimal place except 100% will be displayed without any decimal places and percentages will not be displayed for zero counts.

Continuous data will be summarized using the number of observations (n), mean, standard deviation (SD), median, first quartile, third quartile, minimum, and maximum. Minimum and maximum will be rounded to the precision of the original data. Mean and median will be rounded to 1 decimal place greater than the precision of the original data. The SD will be rounded to 2 decimal places greater than the precision of the original data, up to a maximum of 3 decimal places.

A sensitivity analysis may be carried out at the end of the study if the number of patients impacted by the COVID-19 pandemic is large (e.g. >10% missed injections due to COVID-19) and thought to be impacting the efficacy and safety endpoints. This sensitivity analysis may exclude the patients affected by the pandemic.

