#### 11.5.8.1 CDR-SB

The CDR-SB is a global rating of the function of AD subjects assessed in six categories: memory, orientation, judgement and problem solving, community affairs, home and hobbies and personal care. It is based on a semi-structured interview conducted with the subject and caregiver, by a rater without access to the results of the cognitive tests described above. Each category has scores from 0 (no symptoms) to 3 (severe) and the sum of these items (sum of boxes) may therefore range from 0 to 18 points. The CDR global score is derived from scores of each individual category and will be used as part of the selection criteria (score of 0.5 or 1 at Screening).

Actual values and change from baseline [Week 0 or Screening] will be summarized by Visit (Visit 6 [Week 10], Visit 9 [Week 50] and Visit 11 [Week 74]) and Treatment Group (and overall) for the Intention-to Treat Population [TFL Shell Table 14.3.9].

The CDR-SB data including CDR global score will also be listed for the ITT Population [TFL Shell Listing 16.2.7.10].

Additionally, specific footnote will be included where data on CDR-SB have been collected remotely by telephone interview to specify any details, if needed. Sub-analyses related to the remote mode of administration will not be conducted.

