#### 11.5.8.2 RBANS

The RBANS is a test designed to measure cognitive decline or improvement in a short series of 12 subtests that measure attention, language, visuospatial/constructional abilities, and immediate and delayed memory. The test yields 5 Index scores and a Total Scale score. Normative information from the test manual is used to calculate the Index and Total scores.

RBANS Total Scale Score and change from baseline will be summarized by Visit (Visit 6 [week 10], Visit 9 [Week 50] and Visit 11 [Week 74]) and Treatment Group (and overall) for the Intention-to Treat Population [TFL Shell Table 14.3.10].

The RBANS data will also be listed for the ITT Population [TFL Shell Listing 16.2.7.9].

Additionally, specific footnote will be included where data on RBANS have been collected remotely by telephone interview to specify any details, if needed. Sub-analyses related to the remote mode of administration will not be conducted.

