#### 11.5.8.4 NPI

The NPI is a 12-item scale which assesses domains/behavioral disturbances commonly occurring in dementia subjects. No score will be calculated if there is missing data in any item scale. Twelve domains/behavioral areas are included in the NPI: delusions, hallucinations, agitation/aggression, depression/dysphoria, anxiety, elation/euphoria, apathy/indifference, disinhibition, irritability/lability, aberrant motor behavior, night-time behaviors, and appetite/eating changes. Through a structured interview with the caregiver, each of these 12 domains will be assessed. For each behavior that has not occurred a frequency of 0 will be recorded. For each behavior that is determined to have occurred, the frequency (1: Occasionally, 2: Often, 3: Frequently, 4: Very Frequently) and severity (1: Mild, 2: Moderate, 3: Marked) will be determined. The frequency and severity will be multiplied together to provide a total score. The total NPI score is calculated by summing across all 12 domains/behaviors generating a score which ranges from 0 (no behaviors present) -144 [all behaviors present with greatest frequency (4: Very Frequently) and greatest severity (3: Marked), i.e. 12x4x3]; a higher score indicates more severe psychopathology. Additionally, the caregiver distress for each domain/behavior will be assessed (0: Not at all, 1: Minimally, 2: Mildly, 3: Moderately, 4: Severely, 5: Very severely or extremely). The NPI Total Distress Score is calculated by adding the individual distress scores for the individual domains/behaviors. The NPI Total Distress Score will range from 0 (0: Not at all recorded for each domain/behavior) to 60 (5: Very severely or extremely recorded for each domain/behavior, i.e. 12x5); a higher score indicates greater caregiver distress.

The NPI Total Score and change from baseline will be summarized by Visit (Visit 6 [Week 10], Visit 9 [Week 50] and Visit 11 [Week 74]) and Treatment Group (and overall) for the Intention-to Treat Population [TFL Shell Table 14.3.11.1].

The NPI Total Distress Score and change from baseline will be summarized by Visit (Visit 6 [Week 10], Visit 9 [Week 50] and Visit 11 [Week 74]) and Treatment Group (and overall) for the Intention-to Treat Population [TFL Shell Table 14.3.11.2].

The NPI data will be also listed for the Intention-to Treat Population [TFL Shell Listing 16.2.7.8].

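### The cognitive and clinical scales are meant to verify that the vaccine causes no impairment, but the SAP plans no difference from placebo and no interval for RBANS, CDR-SB or NPI

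*Protocol*

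**What the plan says.** Protocol 2.2.1 and SAP 7.1 list RBANS, CDR-SB and NPI among the primary safety endpoints. Protocol 3.5.4 gives their use. The cognitive tests, apart from checking eligibility, serve "as part of the safety assessments to verify there is no impairment of subject cognitive status that could be related to the study vaccine". A parallel sentence says that the clinical rating scales serve "to verify there is no impairment of subject clinical status that could be related to the study vaccine".

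The planned analysis is descriptive. Protocol 5.3.5.1: "Data will be presented per measurement time and dose group". SAP 11.5.8.1, for CDR-SB: "Actual values and change from baseline [Week 0 or Screening] will be summarized by Visit". SAP 11.5.8.2: "RBANS Total Scale Score and change from baseline will be summarized by Visit". SAP 11.5.8.4: "The NPI Total Score and change from baseline will be summarized by Visit". The statistics for continuous data in SAP 11.0 are n, mean, SD, median, quartiles, minimum and maximum. The same section states "Descriptive summaries will be tabulated by treatment group" and then names five active dose groups without placebo. Protocol 5.3.4 allows placebo subjects to be pooled across sub-cohorts for presentation.

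Elsewhere the plan does state its precision. SAP 11.6.1, 11.6.2 and 11.7.4 give 95% intervals for titers, antibody ratios and volumetric MRI. Protocol 5.3.1 gives upper bounds for an adverse event not seen in six subjects.

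**The concern.** Saying that no impairment related to the vaccine occurred is a causal, no-harm statement. It needs a comparison with placebo and some limit on the harm still compatible with the data. Protocol 1.1.1 describes Alzheimer's disease as progressive, so decline is expected in every arm. Worsening in a vaccine group does not show harm, and a small change does not rule it out.

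The trial has a randomized placebo arm that could answer the question, but the tables as specified stop one step short of using it. At stake is whether the final report can say how large a vaccine-related worsening these scales leave open.

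**Working it through.** **The plan's own safety figures.** Protocol 5.3.1 works with six active subjects per dose.
- Chance of seeing an event with true rate p: 1 − (1 − p)^6. For 1% this is 5.9%, and for 10% it is 46.9% (stated: 6% and 47%).
- Upper bound when none is seen: 1 − (1 − confidence)^(1/6). This gives 23.5% at 80% and 31.9% at 90% (stated: 24% and 32%).

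These reproduce. For the cognitive and clinical scales the documents give no effect size, SD, alpha or margin, so there is no corresponding figure to check.

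**Group sizes.** Sub-cohorts 1.1, 1.3, 2.1 and 2.2 have 8 subjects each. Sub-cohort 1.2 was expanded to 25 (SAP 6.0). Sub-cohort 2.3 and Cohort 3 were not started.
- Total: 8 + 25 + 8 + 8 + 8 = 57.
- Active: 6 + 19 + 6 + 6 + 6 = 43. Placebo: 2 + 6 + 2 + 2 + 2 = 14.
- ACI-35.030 with doses pooled: 6 + 19 + 6 = 31.

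The 19/6 split of the 25 is assumed from 3:1 allocation. The totals ignore dropout and replacements.

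**Precision of a difference from placebo.** In units of the SD of change, the 95% half-width is t(0.975; n1 + n2 − 2) × √(1/n1 + 1/n2).

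| Active v placebo | t | √(1/n1 + 1/n2) | Half-width (SD) |
|---|---|---|---|
| 6 v 14 (one small dose group) | 2.101 | 0.488 | 1.03 |
| 19 v 14 (900 µg) | 2.040 | 0.352 | 0.72 |
| 31 v 14 (all ACI-35.030) | 2.017 | 0.322 | 0.65 |
| 43 v 14 (all active) | 2.004 | 0.308 | 0.62 |
| 6 v 2 (within one sub-cohort) | 2.447 | 0.816 | 2.00 |

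If the observed difference were exactly zero, the harmful-direction limit would equal the half-width. With pooled placebo that is roughly 0.6 to 1 SD. This result needs no assumed effect size.

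**Miss rates, as illustration only.** For a hypothetical two-sided 5% t-test (noncentral t) and an assumed true worsening of 0.5 SD, the chance of a non-significant result is 84% (6 v 14), 72% (19 v 14), 67% (31 v 14), 64% (43 v 14) and 92% (6 v 2). Over 0.3 to 1.0 SD and the same kinds of comparison it runs from about 10% to 95%.

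**A contrast that cannot be estimated.** SAP 12.0 records that Visit 6 was remote for 7 of 8 sub-cohort 1.1 subjects. Protocol 3.5.2.12 lists CDR, NPI and C-SSRS for that remote visit, but not RBANS. At most one subject in that sub-cohort has a Week 26 RBANS, so the 6 v 14 row does not apply there.

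**The case against.** The strongest reply is that this is an early dose-finding study with groups of six, where description is the stated design. No test is planned on these scales, so no miss rate belongs to the plan. A reader might infer that a relevant decline would be missed 70 to 85% of the time. That range describes one dose group against pooled placebo at an assumed 0.5 SD, and no passage calls 0.5 SD the relevant amount.

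A reader might also infer that a lack of visible difference will be read as safety. No passage says so for this trial. Protocol 1.1.2.3 does report the earlier ACI-35 study as showing no evidence of a detrimental effect on these endpoints, but adds that larger studies are needed to explore such effects.

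Nor is placebo absent from the reporting. SAP 9.0 and 9.4 present a placebo arm, and the table shells are in a separate document. The DSMB receives unblinded safety data including cognitive and clinical tables by visit. Subject listings, adverse event reporting, neurological examinations, MRI and CSF markers also look for harm. If placebo is shown, a reader can compute the interval from the n, mean and SD.

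All of that stands, and it limits the point to one of reporting. It does not remove it. The power caveats in Protocol 1.4 and 3.5.6 are attached to efficacy, not to the safety purpose in 3.5.4. The statement that no testing is planned (Protocol 5.3.6.2, SAP 11.6.1) concerns antibody responses. The DSMB table titles show no contrast or bound either.

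**Conclusion.** The point holds as a mismatch between the stated purpose and the planned analysis. Descriptive change per group cannot verify that the vaccine causes no impairment, and the SAP specifies neither a difference from placebo nor an interval for these three primary safety scales. With the assumed 43 active and 14 pooled placebo subjects, such an interval would leave a worsening of about 0.62 SD (all active) to 1.03 SD (a six-subject dose) unexcluded even at an observed difference of zero. Dropout would widen this.

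The documents do not support the stronger statements that harm would be missed at a fixed rate or that silence in the tables will be reported as safety. This is a low-cost improvement to reporting. It does not invalidate the safety monitoring.

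**What to change.** - **SAP 11.0:** name pooled placebo as a treatment column.
- **SAP 11.5.8.1, 11.5.8.2 and 11.5.8.4 (Tables 14.3.9, 14.3.10, 14.3.11.1):** add the difference in mean change from baseline at Weeks 26, 50 and 74 with a t-based 95% interval. The main rows are each vaccine with doses pooled minus pooled placebo; add rows by dose where data allow. Label them descriptive, without multiplicity adjustment.
- **Harmful-direction limit:** report the lower limit for RBANS and the upper limit for CDR-SB and NPI as the largest worsening not excluded.
- **Contrasts that cannot be estimated:** omit them, for example Week 26 RBANS at 300 µg.
- **Interpretation:** state in the SAP that absence of a visible difference will not be reported as absence of impairment.
- **Protocol 3.5.4, at the next amendment:** change the purpose from verifying no impairment to *monitor for and estimate any impairment*.
- **Visit label:** these SAP sections and Protocol 5.3.5.1 label Visit 6 as Week 10, while the schedule has Week 26. Correct this at the same time.

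Cost: no new data. The pooled rows give 2 vaccines × 3 scales × 3 visits = 18 intervals. Adding all five doses would make 7 × 9 = 63, less those that cannot be estimated. The protocol wording needs ethics approval (Protocol 6.1.2), so it should wait for an amendment made for other reasons. The intervals will be wide and the safety statement less favourable.
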